High-risk children are disproportionately of color, have low household levels of education and income, attend poorer performing schools, come from lower socio-economic background.¹⁸ Poorly controlled asthma contributes to poor school performance by disrupting sleep and causing missed days of school^{19,20}, and associations between poor asthma control and missed school are higher among minority children.²¹ Researchers have suggested possible determinants of non-adherence including concerns about medication adverse effects, belief that asthma is not a serious problem, belief that medications are not helping, and preference for a non-pharmacological approach, among others.²² In order to address both the persistent high levels of morbidity associated with asthma and increasing disparities, new approaches to asthma management are needed to more effectively deliver evidence-based preventive treatments and identify children who need a more intensive, stepped up treatment plan. While some interventions based in schools, in the home, or in the community have shown promise,²³⁻²⁵ important limitations have included lack of coordination with community health care providers (HCPs), lack of involvement of schools and the community, inability to monitor medication adherence and lack of sustainability. In short, we aim to reduce health disparities with this program by targeting the highest risk asthma patients, those admitted to the hospital inpatient or emergency department with an asthma exacerbation, which tend to be disproportionately minority patients, and utilize new and innovative technology to improve care for these patients.

III. Preliminary Studies/Progress Report:

We have been conducting a pilot study evaluating the use of electronic adherence monitoring devices in the pediatric asthma population. We have collected preliminary data on the usability of these devices in our population of children aged 6-17. Preliminary evaluation of this data has shown that the devices are largely well tolerated, and data from the devices is accessed often by providers. Most patients feel comfortable utilizing smartphone applications, and the majority of patients found the devices easy to use.

IV. Research Methods

A. Outcome Measure(s):

A table of outcomes to be collected during the study time period is give below (table 1). A detailed description of the outcome follows.

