We will obtain a signed parental permission form and an age-appropriate assent form for participants younger than 18 years. Consent will be obtained by a member of the research team (principally, the research coordinator or a research assistant). It will be made clear to patients that the research team is not part of the treatment team.

Study Design

We plan to enroll a total of 100 patients. and up to 400 providers. Patients enrolled will be provided and trained on using the adherence monitoring prior to discharge (sensors will be placed on discharge controller and quick-relief medication). Participants will also be enrolled in the smartphone application that will give them feedback about their medication usage. Once enrolled in the application, patients will receive push notification reminders to use their medications, as well as be able to access their adherence information in real time. Caretakers will also be given the

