option to have access to their child's adherence information. The smartphone application also has portions dedicated to education about asthma triggers. Patients will be set up with a pulmonary or allergy follow up within 2-4 weeks of discharge. Patient's pulmonary or allergy providers will also be enrolled in the propeller health system, with access to the propeller health dashboard. Once providers receive access, they will be able to log-in and view all of their patients in list format. They will be able to see up to the minute data on patient adherence at any time that they choose to log-in to the dashboard. Providers will also receive email notifications if their patient has not used their controller medications for 7 days, or if their patient has had a significant increase in quick-relief medication use, indicating a worsening of asthma status (see figure 1 below). Patients will be monitored for a total of 3-6 months. The asthma navigator will contact the families at 2, 4 and 6 months post-enrollment, and discuss the patient's recorded adherence with the families. If a patient is enrolled for 4-5 months, we will discuss adherence at 2 and 4/5 months. If a patient is only enrolled for 3 months, we will discuss adherence at 2 and 3 months. Additionally, they will discuss any barriers to adherence that the family may be experiencing, and make referrals to social work as necessary, as well as attempt to brainstorm ways to improve adherence with the families. Additionally, the asthma navigator will collect each patients' adherence data and create an adherence report, which will be distributed on a monthly basis to the patient's primary care provider, pulmonary/allergy provider, and school nurse via email. The asthma navigator will be monitoring communications between the providers and marking the numbers of communications.

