At the time of enrollment, patients will be asked for permission to contact the child's primary care provider and school nurse. If these providers agree to participate in the study, surveys will be sent to all providers of patients (PCPs, school nurses and specialists) to determine if they found the navigator to be helpful, and to see if communication increased due to the intervention. Additionally, the research coordinator will be monitoring the provider portal to ensure that patients' devices are regularly syncing with their phone's Bluetooth, and contact any patients whose devices are not syncing normally. At the study's conclusion, we will plan to have the families return the devices to the research coordinator via US mail. After the conclusion of the study, families will be contacted by the research coordinator to ask if they would be willing to evaluate the navigator via the PSN-I navigator assessment tool. The navigator assessment tool will be used to evaluate utility of the navigator themselves. This is a tool that has been utilized previously in this context to evaluate efficacy of navigator programs. This will only be evaluated at the end of the study. There will be no reimbursement for time for this last survey.

If a patient is having difficulties with syncing their sensors to their phone, we will provide them with a hub to collect the sensor data.

D. Description, Risks and Justification of Procedures and Data Collection Tools:

There will be no medical procedures done during this study. The data collection will occur via surveys, and data collected from the adherence devices. Risks of data collection include accidental disclosure of information, though steps will be taken to prevent this. Also, there is a GPS capability of the devices, so there is a risk of disclosure of patient's location patterns.

E. Potential Scientific Problems:

We are aware that we are underpowered to fully evaluate some of the outcomes that we are interested in obtaining. Additionally, we are limited to single group analysis by request of the funding agency (rather than also having a control group), so we are limited in our ability to make full comparisons. However we would like to undertake this study as a pilot evaluation for the use of the asthma navigator in this population, utilizing adherence monitoring technology to better understand the influence of these evaluations.

F. Data Analysis Plan:

Analysis plan

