The study is limited by time frame and funding for a one year recruitment period. The primary goal of the study is to provide preliminary information on the effect of a navigator program on the patient and caregiver response to asthma disease control. As a pilot and feasibility study, investigators have chosen to enroll a total of 100 patients and up to 400 providers. Through past clinical experience, we know that some months of the year are higher risk for asthma exacerbations, so we expect to screen more patients during the fall and winter than summer or spring. Considering the variable clinical case load Investigators plan on enrolling an average of 10 participants per month. Anticipating an enrollment rate of approximately 20% (in 2015, there were >600 asthma related admissions at Children's Hospital Colorado), investigators state they should be able to enroll up to 100 patients within one year. We plan to enroll up to 4 providers per patient with a simple pre-post survey as well.

The primary hypothesis of interest is to test whether change in adherence rates are different from zero. The smallest detectable difference was based on a paired sample t-test between pre and post adherence scores with a Type I error rate of 0.05 and 90% power. Based on previous studies⁸, investigators assumed a mean adherence rate of 50% with a standard deviation of 22%.

Table X:	
N	Δ
100	8%
65	10%
30	15%

Table X lists the smallest detectable difference (Δ) for by sample size. For the primary aim investigators will be able to detect a change of 8% or more in percent adherence during the study period with the available 100 patients.

F. Summarize Knowledge to be Gained:

- a. **Utility of an asthma navigator in addition to electronic adherence monitoring in improving adherence to asthma medications**
- b. **Utility of an asthma navigator in improving communication amongst all of a patient's medical providers**
- c. **Utility of an asthma navigator in improving other asthma control related outcomes.**

Asthma Control Classification

Control is computed based on taking the entry with the worst outcome in the following age-based tables:

Asthma Control Classification (Age 5-10)

(Age 5-11)	Asthma	Control	Classification
	Well controlled	Not well controlled	Very poorly controlled
Symptoms (manually entered)	≤ 2 days/week but not more than once on each day	> 2 days/week or multiple times on ≤ 2 days/week	Every day in previous week

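### Aim 1 and the knowledge statement credit adherence to the navigator, but with one group and no contrast that isolates the navigator, a gain over historical rates reflects the whole package of monitoring, reminders, alerts, follow-up and navigator.

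*Combined protocol and SAP*

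**What the plan says.** Aim 1 (section I) asks whether adding a navigator to current standard care raises adherence above historical rates. The first item under Summarize Knowledge to be Gained goes a step further and names the "Utility of an asthma navigator in addition to electronic adherence monitoring in improving adherence to asthma medications".

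The Study Design text in section IV.C describes what each child receives besides the navigator. Sensors are fitted before discharge. On the app: "Once enrolled in the application, patients will receive push notification reminders to use their medications". Children can also see their own adherence in real time. A pulmonary or allergy visit is arranged for 2-4 weeks after discharge. Those specialists get a dashboard, and an email if the controller has gone unused for 7 days.

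On the navigator, the same section says: "The asthma navigator will contact the families at 2, 4 and 6 months post-enrollment". The navigator also emails adherence reports each month to primary care, the specialist and the school nurse.

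Table 1 in section IV.A marks no adherence measurement at the admission visit; the first mark is at 2 months. The primary test under Power and Sample Size is whether the change in adherence differs from zero. Section E, Potential Scientific Problems, states: "we are limited to single group analysis by request of the funding agency (rather than also having a control group". It calls the study a pilot and does not discuss the co-interventions.

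**The concern.** Aim 1 and the knowledge item name different comparators: standard care in one, electronic monitoring in the other. The design isolates the navigator against neither. A rise over historical rates could come wholly from reminders, live feedback, alerts or the arranged specialist visit, and the plan's wording would still report it as the value of a navigator. A pilot exists to tell the next trial which component to carry forward. If the credit goes to the wrong one, a follow-on trial could fund navigators when the app was doing the work.

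**Working it through.** **1. The two planned comparisons.**

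| Comparison | Where | What the difference contains |
|---|---|---|
| Study adherence against historical rates | Aim 1 | Sensors, reminders, live feedback, dashboard and alerts, arranged follow-up, and navigator |
| Change within child against zero | Power and Sample Size | Depends on what counts as pre, which the plan does not define. Sensor readings begin only once the device is in place, so none is free of it |

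The Data Analysis Plan lists tests of change during the study and graphs of adherence over time. It defines no monitoring-only group, period or contrast. It mentions summaries by study arm, but there is one arm.

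**2. The plan's own detectable difference.** The inputs, from Power and Sample Size, are a "paired sample t-test between pre and post adherence scores with a Type I error rate of 0.05 and 90% power", and "investigators assumed a mean adherence rate of 50% with a standard deviation of 22"%. The text concludes that "investigators will be able to detect a change of 8% or more in percent adherence during the study period with the available 100 patients". I take the test as two-sided and 22 as the SD of the change; the plan states neither.

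- Normal approximation at N = 100: (1.960 + 1.282) × 22 / √100 = 7.1 points.
- Noncentral t: 7.2, 9.0 and 13.5 points for N = 100, 65 and 30, against 8, 10 and 15 in Table X.
- The table's figures correspond to 95% power (8.01, 9.99, 14.99), or to 90% power with an SD of change of about 24.5.
- With zero correlation the SD of the change is 22 × √2 = 31.1, and the detectable changes are 10.2, 12.7 and 19.1.

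So the 8% is not reproduced from the stated inputs. That is a separate matter: these power figures neither support nor weaken the attribution point. They supply the N and SD for step 3.

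**3. How readily the package alone gives a significant result.** Suppose the navigator has no effect and the other components shift mean adherence by c points from a fixed reference. The test has noncentrality c√N / SD. For N = 100, c = 5 and SD = 22 this is 5 × 10 / 22 = 2.27. Two-sided 0.05:

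| c (assumed) | SD 22 | SD 31.1 |
|---|---|---|
| 2 | 15% | 10% |
| 4 | 44% | 25% |
| 5 | 61% | 36% |
| 8 | 95% | 72% |
| 10 | 99% | 89% |

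The documents give no value for c, so the table shows a range and not an estimate. It assumes no dropout; the plan makes no allowance for any.

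**4. What isolating the navigator would need.** For illustration, take concurrent monitoring-only and monitoring-plus-navigator groups with SD 22, two-sided 0.05 and 90% power. For 8 points, n per group = 2 × (1.960 + 1.282)² × 22² / 8² = 159. Splitting the planned 100 children into 50 and 50 gives a detectable difference of 3.242 × 22 × √(2/50) = 14.3 points.

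**The case against.** The strongest reply is that much of this is already conceded. Section E says that the single group was the funder's requirement, that comparisons are limited, and that the study is a pilot using monitoring technology. The knowledge item itself mentions monitoring, so its use alongside the navigator is disclosed. All of that is true. What is not disclosed is that the effects cannot be told apart, and the knowledge item still poses a navigator-specific question.

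A second reply is that the primary test is change within child, not level against history. If pre meant months 0-2 and post the later months, the app would be held constant across the first family contact. This has force, but pre is undefined and the plan does not commit to that contrast. It would also mix the navigator with other things that change over time. Section II says adherence worsens even under monitoring, and the enrolment text expects seasonal variation in exacerbations. Recovery after an admission is a further possibility. Such a contrast could manufacture an effect or hide one.

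Three stronger readings are tempting, and the documents do not support them:

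- **That the navigator's later start is itself the flaw.** It is not; a defined period of monitoring alone before the first contact could help. The gap is that no such period is planned as a comparator.
- **That children get little navigator exposure.** Time after the first family contact is (3 − 2)/3 = 33% of follow-up for a 3-month child and (6 − 2)/6 = 67% for a 6-month child. These figures cover family contact only. Aim 1's hypothesis also counts supplying adherence rates to the care team. If the first monthly report goes out at month 1 (no date is given), the shares become 2/3 and 5/6.
- **That every other component starts at discharge and every last contact closes monitoring.** No start date is given for provider access or alerts, and the text for 4-5 month children does not fix the last contact at the end. Nor does it say whether the arranged specialist visit is study-added or usual care.

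**Conclusion.** The point holds as one of attribution. A gain over historical rates would be the effect of the combined package, together with any difference between these children and the historical ones, and the plan cannot assign it to the navigator. The trial can run as designed; its stated inference should change. The likely size of a misattributed effect cannot be known from the documents. Under the assumptions in step 3, a co-intervention effect of 5 to 8 points with no navigator effect would be significant with probability 61% to 95% at SD 22, or 36% to 72% at SD 31.1. The conclusion does not depend on those figures. It rests on the single group, the absence of any device-free adherence reading, and the absence of a contrast that isolates the navigator.

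**What to change.** 1. Reword Aim 1, its hypothesis and the first knowledge item so that any difference from historical rates is credited to the package: monitoring app, provider alerts, arranged follow-up and navigator. Add the bundling to section E. This costs wording only and needs no control arm.
2. Optionally, pre-specify an exploratory contrast of each child's sensor adherence before and after the first family contact at about month 2, modelling the month 0-2 trend. State that it estimates the added family contact, not the whole navigator program, because monthly provider reports may start earlier. State also that it stays confounded by declining adherence under monitoring, season and recovery after admission. It uses sensor data already collected.
3. Section III says: "We have been conducting a pilot study evaluating the use of electronic adherence monitoring devices in the pediatric asthma population". Use that pilot as a reference only if it holds comparable adherence data and its app features are known. The section reports usability, tolerability and provider access, but no adherence rate, and does not say whether those children received reminders or alerts.

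The downside is a narrower headline claim.

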	Outcome Measure	Visit 1 (admission visit)	Visit 2 (2 months)	Visit 3 (4 months or end of study)	Visit 4 (6 months or end of
--	-----------------	---------------------------------	-----------------------	--	-----------------------------------

					study)
Aim 1	Adherence (continually monitored during trial)		X	X	X
Aim 2	Communication among providers	X			X
Aim 3	Asthma Related Health outcomes	X	X	X	X

- a. Adherence- measured on adherence monitoring devices. The rate of daily prescribed controller medication use will be monitored. For example, if an individual is prescribed two doses per day and the monitoring device records one doses, then the daily adherence measure will be 1/2 or 50%. The outcome measure will be continuously gathered via the Propeller Health monitoring device ® (Madison, WI). Rate of monthly adherence will be calculated between study visits,
- b. Communication between providers. Communication between providers will be measured in a number of ways. Providers include nurses, parents, physicians and patients. In order to measure any change in communication the following communication metrics will be monitored.
 - i. Number of emails sent between providers will be assessed if email is used as the primary means of communication.
 - ii. A subset of provider teams will possibly be enrolled in asynchronous communication monitoring. This is a method of HIPAA compliant messaging, which involves providers utilizing an application or website, and communicating securely within that platform. We plan to utilize the Stich platform, which is marketed as HIPAA compliant (<https://www.teamstitch.com>). We are currently on a waiting list to possibly test the technology.
 - iii. Providers will be surveyed before and after the intervention to determine if they felt that the navigators adequately improved communication regarding specific patient related issues.
- c. Other asthma related outcomes including asthma control test, symptom assessments, asthma related readmissions or revisits, missed school days, and provider satisfaction.
 - i. Asthma Control Test, a self (or in the case of this study, phone administered)-administered questionnaire with 5 questions which summarizes asthma control, will be used to record asthma control in children 12 or older.
 - ii. Childhood Asthma Control Test (or in the case of this study, phone administered), a parent and child administered questionnaire, will be used to record asthma control for children 6-11 years of age.

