 - iii. Pediatric Inhaler Adherence Questionnaire, a self (or in the case of this study, phone administered) survey of barriers to medication adherence
 - iv. Parent attitudes towards medications and barriers to adherence.
 - v. Changes in adherence barriers and behaviors to improve adherence over time
 - vi. The number of asthma related readmissions or revisits between study visits will be self-reported.

- vii. The number of missed school days between visits will be self-reported.
- viii. Provider satisfaction will be recorded using the pre-post surveys

B. Description of Population to be Enrolled:

- a. Children admitted to Children’s Hospital Colorado inpatient or emergency department with a primary diagnosis of asthma exacerbation.
 - i. Inclusion criteria-patients
 - 1. Age 6-17 years
 - 2. On a controller medication at baseline
 - ii. Inclusion criteria-providers
 - 1. Aged 18-70
 - 2. Caring for a patient that is enrolled in the study
 - iii. Exclusion criteria
 - 1. Primary language other than English or Spanish (smartphone application only available in these languages)
 - 2. Homeschooled or not in school
 - 3. Significant developmental delay, cystic fibrosis, interstitial lung disease, tracheostomy/ventilator dependence
 - 4. Following up with a pulmonary or allergy provider outside of the CHCO system

C. Study Design and Research Methods

The proposed study is a single center trial at Children’s Hospital of Colorado, designed to evaluate the effects of a navigator program on medication adherence, provider communication and other asthma related health outcomes. Participants will be recruited from the population of patients between the age of 6 and 17 years admitted to Children’s Hospital Colorado inpatient or emergency department with a primary diagnosis of asthma exacerbation. Investigators plan on a one-year enrollment period and will follow each study participant for 3-6 months.

Recruitment

Upon admission hospital staff will identify potential participants based on the admission medical record. Patients will be approached by research staff and asked if they would like to participate in the study. A member of the research team (principally, the research coordinator) will do the recruiting. The research coordinator will explain the study and enroll subjects. Estimated duration is 45-60 minutes depending upon the patient.

Consent/Assent

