Demographic information including age, sex, race, and other baseline clinical information upon recruitment including duration of asthma, C-ACT score, ACT score, asthma symptoms, lung function, prescribed medication, and asthma related health care use in the previous year will be obtained at enrollment. The distributions of outcomes will be examined for normality using the Anderson-Darling Test. Dependent upon the distribution we will use the Wilcoxon rank-sum test, Mann-Whitney U test or paired T-test to test for significant changes in outcomes during the study period. Longitudinal patterns of adherence will be examined graphically.

Monthly rates of adherence, asthma symptoms, asthma control scores and monthly missed number of school days and number of hospitalizations will be calculated by study arm. Survey information from patients, caregivers, physicians and navigators on the navigator intervention will be reviewed by study staff and summarized qualitatively. Number of rehospitalizations will be obtained via chart review at 1 month, 6 months and 12 months post hospitalization.

The cost-effectiveness of the navigator intervention will be summarized based on medical resource utilization (direct) and loss of productivity (indirect). Medical resources utilization will include medical care resource utilization, asthma medication variables, navigator time and salary, while loss of productivity will be measured using the number of hours caretaker missed work due to participant's asthma, number of hours dependent participant missed school due to his/her asthma, and number of hours independent participant missed work due to his/her asthma. Unit costs will be applied to healthcare resources and loss of productivity and summed to obtain total costs for each subject. Average costs for the study group will be presented.

Power and Sample Size

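### Follow-up varies from 3 to 6 months, but the paired primary test fixes no pre or post month, and sustained adherence has no criterion

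*Combined protocol and SAP*

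**What the plan says.** IV.C (Study Design and Research Methods) states the length of follow-up twice: the investigators "will follow each study participant for 3-6 months", and "Patients will be monitored for a total of 3-6 months". The same section moves the navigator's calls to suit: months 2, 4 and 6 for a child followed the full time, 2 and 4/5 for one enrolled 4 to 5 months, and 2 and 3 for one enrolled 3 months. Table 1 in IV.A labels one column "Visit 3 (4 months or end of study" and gives Visit 4 the same alternative at 6 months.

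Under Power and Sample Size, the primary hypothesis is that the change in adherence differs from zero. The detectable difference is "based on a paired sample t-test between pre and post adherence scores", where "investigators assumed a mean adherence rate of 50% with a standard deviation of 22" percent. The conclusion for 100 patients is that "investigators will be able to detect a change of 8% or more in percent adherence during the study period".

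The Analysis plan names rank tests or a "paired T-test to test for significant changes in outcomes during the study period", depending on the distribution. On the time course it says "Longitudinal patterns of adherence will be examined graphically", and it also calculates monthly adherence rates. The Aim 1 hypothesis (section I) has two parts: that adherence rises, and that it is sustained over the 3 to 6 months of monitoring. The aim itself names historical rates as the comparator.

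**The concern.** No section says which month or window supplies the pre score or the post score. The sensors are fitted before discharge with the app reminders switched on, so no device reading precedes the programme. The visit labels suggest that post could be the last visit. In that case it comes from month 3, 4, 5 or 6 depending on the child, and the mean change mixes intervals of 2 to 5 months from month 1.

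This matters because section IV.E confines the study to a single group, so no control arm removes a time trend. Section II cites studies in which adherence worsened over time even under monitoring. The estimate would then depend partly on how many children had short follow-up, and the documents do not say what sets a child's length of follow-up.

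The second gap concerns the word sustained. Graphs and monthly means describe the course, and a paired test asks whether the change differs from zero. Neither says how large a fall would still count as sustained, and failing to find a difference does not exclude a real fall.

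**Working it through.** **1. The plan's own figures.** Inputs from Power and Sample Size: two-sided alpha 0.05 (read from a change different from zero), 90% power, SD 22, and Table X giving 8, 10 and 15 points at N = 100, 65 and 30. By paired-t power (noncentral t, n − 1 degrees of freedom):

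- If 22 is the SD of the change, the detectable differences at 90% power are 7.2, 9.0 and 13.5. Table X is reproduced at 95% power instead (8.01, 9.99, 14.99).
- At 90% power, Table X needs an SD of change of 24.44, 24.50 and 24.49. If 22 is the SD of each score, the implied correlation is 1 − SD²/(2 × 22²). For N = 100 this is 1 − 24.44²/968 = 0.38, and the other two rows also give 0.38.

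The documents do not say which reading was meant. The value 0.38 is therefore used below only as the low end of a range.

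**2. Effect of the follow-up mix on an end-of-study estimate.** Take pre as month 1 and post as the last month T, with a steady fall of s points per month. The mean change is −s × Σ p(T) × (T − 1), for T = 3 to 6. The documents give neither s nor the mix p(T), so both are assumed.

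- Mix 40/30/20/10% at 3/4/5/6 months: 0.4×2 + 0.3×3 + 0.2×4 + 0.1×5 = 3.0.
- Mix 10/20/30/40%: 0.1×2 + 0.2×3 + 0.3×4 + 0.4×5 = 4.0.

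| Assumed fall per month | Short-follow-up mix | Long-follow-up mix | Difference |
|---|---|---|---|
| 1 point | −3 | −4 | 1 |
| 2 points | −6 | −8 | 2 |
| 3 points | −9 | −12 | 3 |

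**3. Precision for month 3 to month 6.** Assume 100 children, no other loss, SD 22 per score, and the same correlation r between any two months. Fit month as a factor to all available months by generalised least squares: V = (Σ n_T X_T′ Σ_T⁻¹ X_T)⁻¹, where X_T picks out the first T months and Σ_T = 22²[(1 − r)I + rJ]. Then SE = √(c′Vc) for the contrast c, and the 95% half-width is 1.96 × SE.

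| r | 10/20/30/40 children | 25 at each length | 40/30/20/10 children |
|---|---|---|---|
| 0.38 | 6.6 | 8.0 | 12.0 |
| 0.6 | 5.3 | 6.4 | 9.7 |
| 0.8 | 3.8 | 4.6 | 6.9 |

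Under this correlation structure, month 1 to month 6 has the same SE.

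**4. Does the model earn its place?** Six-month children alone give SE = 22 × √(2(1 − r)/n₆). At r = 0.6 these are 3.11, 3.94 and 6.22 for the three mixes, against 2.71, 3.29 and 4.96 from the model. The model's SEs are 13%, 16% and 20% lower. For month 1 to month 3, where all 100 children can contribute, the paired SE is 22 × √(2 × 0.4/100) = 1.97 and the model SE is also 1.97, so nothing is gained.

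**The case against.** This is a self-described pilot that discloses limited power and the lack of a control group, and a formal margin for sustained adherence is a demand more usual in a confirmatory trial. The illustrated shift is 1 to 3 points on assumed inputs, and only one follow-up mix will occur, which will be known at analysis. A mixed model adds nothing at month 3. Most of this stands. It limits the weight of the point and argues for a descriptive criterion. It does not supply the missing windows, and preliminary information on the programme's effect is the study's stated goal.

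Three stronger readings are tempting, and the documents do not support them.

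- A reader might infer that varying follow-up could create or reverse the result. A 6-month child's expected change does differ from a 3-month child's by 3, 6 or 9 points at falls of 1, 2 or 3 per month (three extra months), and 9 exceeds 8. But that compares single follow-up lengths. Between the two mixes tried, the mean moves 1 to 3 points and keeps its sign.
- A reader might infer that the time course is only plotted. Monthly rates are also calculated, and if pre is month 1 and post the last month, the planned paired test is itself a test of change. What is missing is a criterion.
- A reader might take 0.38 as the plan's correlation. Table X fits equally well with 22 as the SD of the change and 95% power.

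**Conclusion.** The point holds as a cheap improvement. Follow-up varies by design, and neither pre nor post is dated. Under an end-of-study reading, the primary estimate pools different intervals; the illustrated consequence is 1 to 3 points against a detectable 8, given an assumed linear fall and two assumed mixes. The larger practical gap is that nothing planned can show adherence to be sustained. The interval that could do so has a half-width of about 4 to 12 points over correlations of 0.38 to 0.8 and the three mixes, assuming SD 22 and 100 children. It may therefore be too wide to exclude even an 8-point fall, which is a reason to report it rather than rely on a flat plot. None of this invalidates the pilot.

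**What to change.** 1. Fix the two windows of the primary paired test in advance, for example month 1 and month 3. Every planned schedule reaches month 3, before dropout or syncing loss. The primary month is the sponsor's choice: month 6 is observed only in children followed that long, and the last scheduled call falls at about its close. If only month 3 is wanted, one sentence is enough and no model is needed.
2. For sustained adherence, fit the monthly rates already calculated with a repeated-measures model (month as a factor, all available months per child). Report the month 1 to month 6 and month 3 to month 6 changes with 95% confidence intervals, read against a tolerable fall stated beforehand, as a descriptive pilot criterion.
3. State that month 1 is already under reminders and monitoring, so these contrasts measure change during the programme and not improvement over the historical rates named in Aim 1. That comparison needs its own stated source.

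The cost is slightly more analysis and wording, with no new data. The model brings a covariance assumption and a missing-at-random assumption for children with shorter follow-up. The second is easier to judge if the protocol says what determines each child's length of follow-up.
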